### ***5.7 Information about the study results***

The study report will include all the study analysis performed and will be provided to the participating investigators if needed.

## **6. Study timetable**

Depending on countries/sites, the study will take place starting in the first quarter 2011 and patient recruitment will last until the second quarter of 2014. Patients will be followed over a two year period after DOTAREM® administration.

## **7. Regulatory issues/ Quality Assurance**

The study will be conducted in each participating country in accordance with the local regulations in force.

The patient will be orally asked if he/she agrees to participating in the study and informed about the study objectives and design. Patient's consent procedures will be followed according to each country's regulatory requirements.

The Sponsor reserves the right to perform an audit of the study data in order to verify the quality of their collection, their security and their integrity.

Each participating physician will sign a financial agreement specifying his/her commitment to respect the study protocol and the amount of fees that he/she will receive for the study.

## **8. Confidentiality**

The physician and all staff involved must respect professional secrecy regarding the nature of the product studied, the way in which the study is carried out, the people participating and the study results obtained.

No information that could allow an identification of the patient identity will be collected. Patient confidentiality will be maintained at all time (by Sponsor, Clinical Research Organisation, Regulatory Authorities, Ethics Committees).

## **9. Publications**

The study data are the exclusive property of the Sponsor. No data can be published by the physician without prior approval by the Sponsor in writing. The modalities concerning the publications and the presentations about the study results will be defined by the Sponsor.

**12. Appendices**

Appendix 1: Form related to site characteristics and radiological activities

Appendix 2: Patient general questionnaire

Appendix 3: Patient FUP questionnaire.

Appendix 4: Suspect Adverse Reaction Report (F006031)

Appendix 5: Patient Information Sheet

1. SUMMARY OF THE STUDY PROTOCOL

This document presents the statistical analysis plan (SAP) for Guerbet, Protocol No. DGD-55-003: **“Observational study on the incidence of NSF in renal impaired patients following DOTAREM® administration”**.

This analysis plan is based on the final protocol Version 1.0 dated November 08, 2010 + protocol amendment 1 dated July 24, 2012.

1.1. Study objectives

The primary objective of this study is to prospectively estimate the incidence of NSF in patients with moderate to severe renal impairment after administration of DOTAREM®. Patients will be followed during a two-year period after administration of DOTAREM®, to assess if signs or symptoms suggestive of NSF have appeared.

The secondary objectives of the study are:

- to collect a large number of data concerning the general safety profile of DOTAREM® during patient inclusion and MR examination,
- to collect information regarding MRI indication,
- to collect conditions of use/administration of the product in this specific population of patients,
- to collect efficacy data (image and diagnostic quality).

1.2. Study design

DGD-55-003 is a prospective multinational, multicenter, observational Post-Marketing Study (PMS) including longitudinal safety follow-ups. The number of sites and patients will vary from one country to another.

Patients included in the study should have moderate (eGFR of 30-59 ml/min/1.73 m²) to severe (eGFR<30 ml/min/1.73 m²) and end stage (eGFR<15 ml/min/1.73 m²) renal impairment or dialysis and should be scheduled for a contrast-enhanced MRI with DOTAREM®.

After a patient has satisfied all eligibility requirements, he will undergo a MRI examination with a DOTAREM® administration. All patients will be followed up during 2 years after DOTAREM® administration to collect data on any suspected NSF or NSF related symptoms.

The images will be assessed on-site by the same investigator at each participating hospital.

Safety assessments will include adverse events that occurred during the MRI examination or during the time of usual follow-up post DOTAREM® administration.

CONFIDENTIAL	FORM STATISTICAL ANALYSIS PLAN N° DGD-55-003 VERSION N° 2 DATED: 26 FEBRUARY 2018 (REF I011622)	F015830-01 Page 7 / 49
--------------	--	---------------------------

1.3. Study contrast media

DOTAREM® (gadoterate meglumine)

CONFIDENTIAL	FORM STATISTICAL ANALYSIS PLAN N° DGD-55-003 VERSION N° 2 DATED: 26 FEBRUARY 2018 (REF I011622)	F015830-01 Page 8 / 49
--------------	---	---------------------------

2. EVALUATION CRITERIA

2.1. Demographic and other baseline characteristics

Demographic variables collected for this study are:

- Age in years for patient more than 2 years old and age in months otherwise,
- height,
- weight,
- sex.

Baseline characteristics collected for this study are:

- Magnetic field,
- Current renal status according to the investigator,
- Most recent serum creatinine before inclusion (in mg/L or mg/dL or μ mol/L),
- Estimated creatinine clearance for children less than 2 years old and eGFR otherwise,
- Pre-existing risk factors and medical history,
- Previous examinations with GBCA,
- Concomitant treatment and recent surgery (<2 years),
- Indication of MRI examination,
- Premedication.

2.2. Efficacy criteria

The primary objective of the study is related to the NSF prevalence and therefore the primary criterion is not an efficacy criterion.

Efficacy variables are derived from the investigator evaluations of the imaging examination. Images will be rated regarding the following items:

- Image quality
- Diagnostic quality

2.3. Safety criteria

Safety variables collected for this study are:

- Modalities of DOTAREM® administration
 - Volume injected,
 - Type of injection,
 - Number of injections,
 - Nature of package
- From DOTAREM® administration until end of usual follow up in the MR unit
 - Adverse events,
 - Serious adverse events,
 - Adverse events requiring the administration of a concomitant drug,
 - Adverse events according to intensity and outcome,
 - Adverse events related to contrast media injection.
- During the follow-up period

CONFIDENTIAL	FORM STATISTICAL ANALYSIS PLAN N° DGD-55-003 VERSION N° 2 DATED: 26 FEBRUARY 2018 (REF I011622)	F015830-01 Page 9 / 49
--------------	--	---------------------------

- Suspicion of NSF and final diagnosis of NSF,
- Medical events,
- Serum creatinine measurements.

2.4. Other criteria

None

CONFIDENTIAL	FORM STATISTICAL ANALYSIS PLAN N° DGD-55-003 VERSION N° 2 DATED: 26 FEBRUARY 2018 (REF I011622)	F015830-01 Page 10 / 49
--------------	---	----------------------------

3. STATISTICAL METHODS

3.1. General considerations

At the end of the study, after the database lock, the statistical analysis will be performed by GUERBET Biostatistic team on the basis of the present document.

A quality control of the statistical analysis will be performed to ensure the reliability of the results.

Thorough description of all parameters reported will be presented. Summary tabulated results will be provided by assessment time if relevant or they will be replaced by the corresponding individual data listings if too few patients are concerned.

Tabulations of quantitative parameters will include the following summary statistics: Number of Patients / Mean / Standard Deviation / Minimum / Median / Maximum. If for a given parameter, the raw value has been collected with x decimal places, the mean, median and standard deviation will be rounded to x+1 decimal places, while the minimum and maximum values will be tabulated as reported with x decimal places.

Tabulations of frequencies for categorical data will include all possible categories and will display the number of observations in a category as well as the percentage (%). Percentages will be rounded to one decimal place. The category missing will be displayed only if there are actually missing values. Percentages will be calculated on the total of recorded (non missing) data.

The **baseline value** will be defined as the last available value prior to administration of the investigational product.

No statistical tests will be performed in this study. All statistics will be only descriptive.

SAS® Version: 9.4 will be used for all descriptive summaries.

3.2. Null and alternative hypothesis

None as no statistical test will be performed in this study.

3.3. Determination of sample size

This study aims at accurately estimating the incidence of the NSF in renal impaired patients, in case such an event is observed after injection of DOTAREM®. Assuming that when exposed to GBCA, the frequency of NSF is ranging from 0% to 4% in this population (maximum frequency being observed with linear GBCA), with a sample size of 1000 patients, a two-sided 95% exact confidence interval for a single proportion will allow to estimate with an adequate accuracy the frequency of this event according to the following table:

CONFIDENTIAL	FORM STATISTICAL ANALYSIS PLAN N° DGD-55-003 VERSION N° 2 DATED: 26 FEBRUARY 2018 (REF I011622)	F015830-01 Page 11 / 49
--------------	---	----------------------------

Observed cases	N	Observed frequency	Exact 95% IC
0	1000	0.0%	0.00% - 0.37%
1	1000	0.1%	0.00% - 0.56%
2	1000	0.2%	0.02% - 0.72%
5	1000	0.5%	0.16% - 1.16%
10	1000	1.0%	0.48% - 1.83%
15	1000	1.5%	0.84% - 2.46%
20	1000	2.0%	1.23% - 3.07%
30	1000	3.0%	2.03% - 4.26%

The sample size of 1000 patients was not reached before the end of the enrolment period (see section 4)

3.4. Adjustment for covariates

Not applicable

3.5. Handling of dropouts or missing data

If the start date of an adverse event is missing, then the adverse event occurs after the DOTAREM® injection.

No replacement of missing data is planned in this study.

3.6. Interim analyses and data monitoring

Not applicable

3.7. Multicentre studies

Number of patients included in each centre will be presented but no demographic parameters, baseline characteristics, efficacy or safety criteria will be presented by centre.

3.8. Multiple comparisons/Multiplicity

Not applicable

3.9. Use of an “efficacy subset” of patients

Efficacy results will be presented using the set of patients having an available diagnostic assessment.

3.10. Active control studies intended to show equivalence

Not applicable

3.11. Examinations of subgroups

Not applicable

CONFIDENTIAL	FORM STATISTICAL ANALYSIS PLAN N° DGD-55-003 VERSION N° 2 DATED: 26 FEBRUARY 2018 (REF I011622)	F015830-01 Page 12 / 49
--------------	--	----------------------------

4. CHANGES IN THE CONDUCT OF THE STUDY OR PLANNED ANALYSES

The protocol was amended on one occurrence globally and twice in Turkey and twice in the United State of America (see protocol amendments for a full list of changes).

The global amendment has introduced following changes:

- The minimum number of patients with severe renal impairment was changed from 50% to 40% but this does not change the planned analysis as no analysis is foreseen considering the renal impairment status.
- The period of recruitment was extended. Initially 1000 patients were supposed to be included in the study with a minimum of 50% of patients with severe renal impairment. Despite the extension of the recruitment period, the sample size of 1000 patients was not reached by the end of the recruitment period. Thanks to better understanding of causality and risk factors conducting to NSF occurrence, safety and educational measures starting from 2012, the rate of NSF appears to be less than 1%, and the study was no longer powered to assess the NSF rate. For this reason and taken into account that the NSF was not a safety priority for the competent authorities anymore due to the low incidence, the recruitment was stopped in March 2015.
- Patients who had received DOTAREM® within 12 months prior to inclusion were included in the study.

The methodology of statistical testing is described in the protocol although no comparison is possible. No statistical tests will be presented in the report.

CONFIDENTIAL	FORM STATISTICAL ANALYSIS PLAN N° DGD-55-003 VERSION N° 2 DATED: 26 FEBRUARY 2018 (REF I011622)	F015830-01 Page 13 / 49
--------------	---	----------------------------

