The good tolerance of DOTAREM® is probably to be credited to the very high thermodynamic stability of the DOTAREM® macrocyclic complex where the toxicity of free Gd3+ ions is reduced by the ligand, DOTA, which has eight coordination sites for chelation. Due to this very high thermodynamic stability, there is no need of an excess of ligand which is used in certain Gadolinium contrast agent preparations to ensure absence of free Gd3+ in solution. DOTAREM® elimination is essentially renal by free glomerular filtration; its half time is comparable to iodinated contrast agents.

Several other Gadolinium complexes with various chemical structures are commercialized apart from DOTAREM®. Most of them have a linear structure and consequently a lower thermodynamic stability than DOTAREM® which is the only Gadolinium chelate to be macrocyclic and ionic.

Although Gadolinium-Based Contrast Agents (GBCA) are generally regarded as non-nephrotoxic in a healthy population, the safety issue of these agents remains controversial in the high-risk patients group and some studies recently suggested a potential risk of gadolinium-induced nephropathy in severe renal impaired patients. In addition, it has been reported recently that a rare serious adverse reaction called Nephrogenic Systemic Fibrosis (NSF) may occur after exposure to gadolinium contrast agents in severe renal impaired patients. This new pathology was first described in the medical literature in 2000^6 and to date, several hundred cases have been diagnosed worldwide. In 2006, the link between NSF and gadolinium-based

contrast agents was made. NSF is characterized by extensive thickening and hardening of the skin associated with skin-colored to erythematous papules that coalesce into erythematous to brawny plaques. Nodules are sometimes also described, flexion contractures with an accompanying limitation of range of motion can also occur. It seems that Gadolinium complexes with high thermodynamic stability such as DOTAREM® have lower risk of being associated with NSF and that the vast majority of published NSF cases were associated with linear compounds.

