At present, the highest incidence of NSF in the high risk renal impaired population is estimated around 3-4 % for Gadodiamide, a linear Gadolinium complex with the lowest thermodynamic and kinetic stabilities among the Gadolinium chelates, but seems to be variable from one product to another. The European Medicines Agency and recently the Food and Drug Administration have classified the gadolinium-containing contrast agents in three groups according to NSF risk based on their thermodynamic and kinetic properties. DOTAREM® was placed in the low risk group.

To date, DOTAREM® is considered as one of the contrast agents with the lowest risk of NSF. In order to confirm this low risk, the incidence of NSF after injection of DOTAREM® must therefore be determined not only in patients with severe renal impairment, but also in patients with moderate renal impairment in order to provide an estimate covering a large population of renal impaired patients.

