## **2. Study objectives**

The main purpose of this study is to prospectively estimate the incidence of NSF in patients with moderate to severe renal impairment after administration of DOTAREM®. Secondarily, to collect a large number of data concerning the general safety profile of DOTAREM®, MRI indication, and conditions of use/administration of the product in this specific population of patients.

In addition, efficacy data (image and diagnostic quality) will also be recorded and described. Regarding the safety profile of DOTAREM®, several follow-ups will be performed. After administration of DOTAREM®, patients will be followed during a two year period to assess if signs or symptoms suggestive of NSF have appeared.

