## **3. Study design and methods**

This observational Post Marketing Study (PMS) is a prospective transversal study including longitudinal safety follow-ups. This study will be performed in several European and non European countries. The sample size to be included is 1,000 patients with a minimum of 40% of patients with severe renal impairment. The number of sites and patients will vary from one country to another.

Fifty centres will be selected worldwide and each centre will be able to include about twenty patients. Three to 5 centres will therefore be selected in each country, i.e. a potential recruitment of 60 to 100 patients per country.

This study will not modify the relationship between the patient and his/her physician(s), or the management of the patient follow-up. The patient will be orally asked if he/she agrees to participating in the study and provided with an information sheet about the study objectives and design, following local regulations. Patient's consent procedures will be followed according to each country's regulatory requirements.

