- If there is any suspicion of NSF

In case of NSF suspicion, a biopsy could be decided by the medical team as a part of the normal patient follow-up in order to confirm or not the diagnosis of NSF. In such a situation, the biopsy results will be collected in a follow-up form.

If any case of suspicion/diagnosis of NSF, the physician in charge of the patient management will promptly inform the local Sponsor (local pharmacovigilance contact) using the dedicated “Suspect Adverse Reaction report” (F006031-See appendix).

Three follow up visits will have to be reported as described below respecting patients' usual follow-up visits:

[figure not shown]
- FUP1: a visit occurring between 3 and 12 months
- FUP2: a visit occurring between 13 and 21 months
- FUP3: a visit occurring between 22 and 27months

Please note that there should be at least 3 months difference between each Follow-up visit reported in order to avoid redundant visits.

If no information could be obtained during the first year after DOTAREM administration from the patient, the physician in charge of the follow-up will be requested to check the hospital/medical notes of the patient and complete a follow up visit form with the data from the hospital notes. This will be requested again during the second year after the DOTAREM administration for the second follow-up and for the last follow-up as well.

The electronic questionnaire for patients of the same centre will be accessible by all investigators of the centre by using personalized logins and passwords. The electronic data collection system also allows follow-up of the changes made by each user.

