### **5.4 Data analysis for global population**

The minimum number of patients included in this study will be 1000 (see next section). Several levels of aggregating patient data will be explored in the statistical analysis and summarized statistics will be reported at :

- centre level within countries;
- country level;
- overall (adjusted on countries if the heterogeneity between countries is too high).

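### NSF is to be reported only for the pooled cohort; one descriptive NSF table by recorded renal status would be a cheap improvement (not a protocol breach)

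*SAP*

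**What the plan says.** **On pooling.** Protocol section 2 sets one aim, to "prospectively estimate the incidence of NSF in patients with moderate to severe renal impairment", and SAP 1.1 repeats it. Protocol 5.4 names centre, country and overall as the levels at which data are summarised. Renal status is not among them.

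**On severity.** Protocol section 1 says that NSF "may occur after exposure to gadolinium contrast agents in severe renal impaired patients", and that its incidence after DOTAREM "must therefore be determined not only in patients with severe renal impairment, but also in patients with moderate renal impairment". The same sentence ends with its purpose, which is an estimate that covers a broad renal-impaired population. Protocol section 3 plans "1,000 patients with a minimum of 40% of patients with severe renal impairment".

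**On the analysis.** SAP section 4 records that this minimum was lowered from 50% and comments that "this does not change the planned analysis as no analysis is foreseen considering the renal impairment status". SAP 3.11 marks subgroup examination as not applicable. SAP 5.6.2 and the shells of Tables 14.3.2.1 and 14.3.2.2 give NSF as counts and percentages in a single Total column, with no confidence interval.

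**On the data.** SAP 2.1 lists "Current renal status according to the investigator" as a baseline item. Table 14.1.4.3 tabulates it as moderate, severe, end stage or dialysis, and kidney transplantation. Listing 16.2.4.3 shows it by patient together with eGFR. Listing 16.2.9.1 shows NSF suspicion and diagnosis by patient, without a renal status column.

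**The concern.** The protocol singles out severe impairment twice: as the setting in which NSF is described, and through a recruitment minimum that was important enough to be changed by amendment. The plan records renal status but never crosses it with the primary endpoint. The report will therefore contain no tabulated NSF result, and no interval, for severe patients.

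Precision is what is at stake. A low or zero pooled count is easily carried over to severe patients as if it were known equally well for them. A table by status with intervals would show how much less is known about that group.

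**Working it through.** **1. Reproduce the plan's figure.** SAP 3.3 uses the exact (Clopper-Pearson) two-sided 95% interval for a single proportion. For x cases in n patients the limits are the beta quantiles Beta(0.025; x, n−x+1) and Beta(0.975; x+1, n−x). For x = 0 the lower limit is 0 and the upper limit is 1 − 0.025^(1/n). With n = 1000 this is 1 − 0.025^(1/1000) = 0.368%, which is the SAP's 0.37%. The other seven rows of the SAP table also reproduce to two decimals.

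**2. Class sizes.** At the planned size and the 40% minimum: 0.40 × 1000 = 400 severe, leaving 600. SAP 3.3 says that 1,000 was not reached, and the documents do not give the achieved number. The smaller totals below are assumptions, each at 40% severe.

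**3. Upper 95% limit with zero cases.**

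| Total (severe / rest) | Pooled | Severe | Rest |
|---|---|---|---|
| 1000 (400 / 600), planned | 0.37% | 0.92% | 0.61% |
| 800 (320 / 480), assumed | 0.46% | 1.15% | 0.77% |
| 600 (240 / 360), assumed | 0.61% | 1.53% | 1.02% |
| 400 (160 / 240), assumed | 0.92% | 2.28% | 1.53% |

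At the planned size the severe limit is 0.918 / 0.368 = 2.5 times the pooled one. For scale, SAP section 4 remarks that the NSF rate now appears to be below 1%. With zero cases at the planned size, both limits lie under 1%. At an assumed total of 600, only the pooled limit does.

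**4. One severe case instead of none.** The exact intervals are 0.006% to 1.385% with 400 severe patients, 0.011% to 2.300% with 240, and 0.016% to 3.433% with 160.

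**5. Small classes.** The upper limit for 0 of 50 is 7.11%, and for 0 of 25 it is 13.72%.

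**6. Denominators.** Table 14.3.2.1 takes percentages over patients with a non-missing NSF entry. Table 14.3.2.2 gives the final diagnosis only among biopsied patients, and Protocol 3.3 leaves biopsy to the medical team. Dividing by the whole safety population would count unassessed patients as free of NSF and make the upper limits too low. The class sizes in Table 14.1.4.3 are therefore not the right denominators.

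**7. Mapping of categories.** The protocol's severe band (eGFR below 30) contains end stage (below 15). Table 14.1.4.3 separates the two and adds kidney transplantation, which carries no severity. Severe plus end stage or dialysis is thus the nearest match to the protocol's severe group by recorded status.

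**8. Timing.** SAP section 4 puts the end of recruitment in March 2015, and the last follow-up is "FUP3: a visit occurring between 22 and 27months". March 2015 + 27 months = June 2017, about 8 months before the SAP of 26 February 2018. SAP 5.1 already refers to follow-up results and SAP 5.4 to a value in the database. A table added now comes later still.

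**The case against.** The strongest case against is that the SAP does what the protocol asks. The objective is a single estimate in moderate to severe impairment, the precision table is for 1,000 patients as one group, and the listed aggregation levels omit renal status. The background sentence naming both severity groups ends by asking for an estimate over a broad population, and the 40% minimum can be read as controlling case mix. All of this stands, and it is why the point is an improvement and not a breach.

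Next, the result can be rebuilt. If the pooled count is zero, every class has zero cases and the class sizes are printed. If there are a few cases, Listings 16.2.9.1 and 16.2.4.3 show each patient's status, and SAP 3.1 allows listings to replace tables when few patients are concerned. This stands in part. The non-missing NSF denominator is not given by class, no interval is planned, and rebuilding means merging two listings patient by patient.

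It is also fair to say that intervals by class would look odd while the pooled result has none, although Protocol 5.2 asks for 95% intervals on estimates. The table should therefore carry the pooled interval too.

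Finally, the addition would be late and some rows very imprecise. Both are true and should be stated on the table. The row categories are those already recorded at baseline, so they are not chosen from the outcome.

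**Conclusion.** The point holds as a cheap and worthwhile improvement. The pooled result is in line with the protocol, and SAP section 4 states the choice openly. What is missing is a tabulated NSF result with its precision for severe patients. With zero cases that precision is an upper limit of 0.92% against 0.37% pooled at the planned size, and 1.53% against 0.61% if 600 had been included. These figures rest on exactly 40% severe and a complete NSF assessment. A higher severe share would narrow the severe interval, and missing assessments would widen it.

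A reader might infer three stronger things that the documents do not support:

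- **That the protocol promises separate severe and moderate estimates.** Its background sentence asks for one estimate with wide coverage, and its analysis section lists no level by severity.
- **That the report will hold no NSF information on severe patients.** Table 14.1.4.3 and the two listings allow a reconstruction.
- **That the pooled percentage is wrong or misleading.** No pooled NSF interval is planned that could mislead, and the documents give no risk ratio between moderate and severe impairment from which to claim dilution.

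**What to change.** Replace the not-applicable entry in SAP 3.11 and the matching remark in section 4 with a statement that NSF is also described by recorded renal status. Add one descriptive table to SAP 6.2.3.2, with its shell in 7.2, in the safety population:

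- **Rows:** overall; moderate; severe; end stage or dialysis; kidney transplantation; missing; and one row combining severe with end stage or dialysis by recorded status. Keep transplanted patients in their own row, and footnote how many have a listed baseline eGFR below 30.
- **Columns, in every row including the overall one:** class size, number with a non-missing NSF assessment (the denominator of Table 14.3.2.1), cases, and the exact two-sided 95% interval. Use two decimals, as an exception to the one-decimal rule for percentages in SAP 3.1.
- **Endpoints:** suspected NSF and finally diagnosed NSF on the same denominator. Show patients suspected but not biopsied separately, not as free of NSF.
- **Limits:** no tests and no comparisons between classes. Label the table as descriptive and added after SAP version 2 (26 February 2018), when follow-up data had already been seen.

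The cost is one table from items already recorded, with no new data and no protocol amendment. The drawbacks are wide intervals in small classes and the late, non-prespecified status of the addition.

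### SAP 4 blames a low NSF rate for the study being no longer powered, but precision was lost through the recruitment shortfall, and limits are given only for N=1000

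*SAP*

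**What the plan says.** The protocol's Background gives the aim: "In order to confirm this low risk, the incidence of NSF after injection of DOTAREM® must therefore be determined". Protocol 2 and SAP 1.1 state the primary objective as estimating incidence. On hypotheses, SAP 3.2 says: "None as no statistical test will be performed in this study".

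SAP 3.3 assumes that "the frequency of NSF is ranging from 0% to 4% in this population" and says of the planned N that "a two-sided 95% exact confidence interval for a single proportion will allow to estimate with an adequate accuracy the frequency of this event". The table that follows covers 0, 1, 2, 5, 10, 15, 20 and 30 cases, all at N=1000. It is followed by the note: "The sample size of 1000 patients was not reached before the end of the enrolment period". The note refers to SAP 4.

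SAP 4 gives no achieved N and no revised limits. It says that, despite an extension, 1000 was not reached, and then that "the rate of NSF appears to be less than 1%, and the study was no longer powered to assess the NSF rate". With NSF no longer being a safety priority for the authorities, this is the reason given for stopping recruitment in March 2015.

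For the primary endpoint, SAP 5.6.2 and Tables 14.3.2.1 and 14.3.2.2 plan counts and percentages without a confidence interval. Protocol 5.2 promises two-sided 95% intervals for estimates.

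**The concern.** The explanation does not fit the design. There is no test whose power could be lost, and rates below 1% were in the planned range from the start and were counted as adequately estimated. What changed was N, and its effect is not quantified anywhere.

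Two misreadings become possible. A result of no cases could be set aside as uninformative because the plan says that the study cannot assess the rate. Or it could be read against the only limit in the SAP, 0.37%, which belongs to a cohort that was not recruited.

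**Working it through.** **Inputs.** Exact two-sided 95% interval for a single proportion, N=1000, rates of 0% to 4% (Protocol 5.5, SAP 3.3). An acceptable loss of 100 patients, leaving 900 (Protocol 5.6). A minimum of 40% with severe impairment (Protocol 3). The achieved N is not stated, so a range of 300 to 1000 is assumed.

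**Formulas.** For x cases in n patients, the lower limit is the 0.025 quantile of Beta(x, n−x+1) and the upper limit is the 0.975 quantile of Beta(x+1, n−x). With x=0 the upper limit is 1 − 0.025^(1/n). The chance of at least one case at true rate p is 1 − (1−p)^n.

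**Step 1: reproduce the SAP table.** At N=1000 all eight intervals reproduce to two decimals. For example, 0 cases gives 1 − 0.025^(1/1000) = 0.368%, 1 case gives an upper limit of 0.556%, and 30 cases gives 2.03% to 4.26%.

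**Step 2: does a low rate cost absolute precision?** The largest distance from the observed rate to a limit at N=1000, from the same table, is:

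| Observed rate | Upper limit | Distance (points) |
|---|---|---|
| 3.0% | 4.26% | 1.26 |
| 2.0% | 3.07% | 1.07 |
| 1.0% | 1.83% | 0.83 |
| 0.5% | 1.16% | 0.66 |
| 0.2% | 0.72% | 0.52 |
| 0.1% | 0.56% | 0.46 |
| 0.0% | 0.37% | 0.37 |

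The distance shrinks as the rate falls. The accuracy column of Protocol 5.5 shows the same: 1.3% at a rate of 3%, 0.8% at 1% and 0.4% at 0%.

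**Step 3: what does a low rate cost?** It costs relative precision. The upper limit is 4.26/3.0 = 1.4 times the estimate at 30 cases, but 0.56/0.1 = 5.6 times at 1 case. It also lowers the chance of seeing a case, as the last three columns below show.

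**Step 4: what does a smaller N cost?**

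| N (assumed below 1000) | Upper limit, 0 cases | P(at least 1 case), true 0.1% | true 0.2% | true 0.5% |
|---|---|---|---|---|
| 1000 | 0.37% | 63% | 86% | 99% |
| 900 | 0.41% | 59% | 83% | 99% |
| 800 | 0.46% | 55% | 80% | 98% |
| 600 | 0.61% | 45% | 70% | 95% |
| 500 | 0.74% | 39% | 63% | 92% |
| 400 | 0.92% | 33% | 55% | 87% |
| 300 | 1.22% | 26% | 45% | 78% |

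The smallest N at which 0 cases excludes 1% is 368 (limit 0.997%; at 367 it is 1.0001%). A single case moves the limit further: 0.79% at N=700, 1.11% at 500 and 1.84% at 300.

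**Step 5: the severe subgroup.** If exactly 40% are severe, N=1000 gives 400 severe patients (0-case limit 0.92%), N=400 gives 160 (2.28%) and N=300 gives 120 (3.03%).

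**The case against.** The best defence is that powered was meant as the chance of observing a case. Protocol 5.5 is headed as a power calculation and its table has a Poisson column for that probability, though its values are not legible in the text available. Protocol 5.6 also speaks of a minimum observable frequency, 0.1% in 1,000 and 0.111% (1/900) after a loss of 100. This stands in part: the chance of seeing a case and the relative precision do fall at low rates. But a rate described only as below 1% does not by itself remove that chance, which is 99% at a true 0.5% with N=1000, and the SAP table no longer carries the Poisson column.

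A second defence is that the clause directly follows the statement that 1000 was not reached, so a lower rate combined with a smaller cohort may be what was meant. That is a fair reading, and the N=1000 table cannot rule it out. The clause nevertheless names only the rate, and no N is given.

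A reader might infer more than the documents support:

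- That the SAP statement is plainly false. It is misleading rather than false, for the reasons above.
- That recruitment ended early. It did so only relative to N=1000. Protocol 6 planned recruitment until the second quarter of 2014, and it stopped in March 2015.
- That any zero-case limit is comfortably below the 3-4% that the protocol quotes for gadodiamide. That figure is for a high-risk renally impaired population, while only 40% of this cohort need have severe impairment. Step 5 shows how little room a small severe subgroup could leave.
- That the report will quote 0.37%. No passage plans this. The risk is that no other limit is on offer.

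**Conclusion.** The concern holds in limited form. The low rate alone does not explain why the study could not assess NSF. Absolute precision was lost through the shortfall, and the study can still put an upper limit on the rate. The limits in SAP 3.3 are for an N that the SAP admits was not reached, and nothing replaces them.

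The size depends on the unknown N. With 0 cases, the limit rises from 0.37% to between 0.41% (N=900) and 1.22% (N=300), and 1% is excluded only with at least 368 evaluable patients. These figures assume exact binomial limits and that every patient counted could have had NSF detected. The second assumption is generous at the safety-population N, because SAP 5.2 requires only one injection for membership and so admits patients with no follow-up. No endpoint or population definition has to change.

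**What to change.** - **SAP 4:** reword the clause to say that precision is reduced because N is below 1000, and that the study can still put an upper limit on the NSF rate. State the achieved N. The SAP is dated February 2018, after recruitment ended.
- **SAP 3.3:** keep the N=1000 table as the planning basis. Beside it, recalculate the exact limits at the actual safety-population N and at the number with follow-up, and say how follow-up is defined. Table 14.1.1.2 already counts included patients with at least one follow-up visit.
- **SAP 5.6.2 and its tables:** report the exact two-sided 95% confidence interval for the observed NSF proportion on both denominators, as Protocol 5.2 promises. Table 14.3.2.2 now takes the final-diagnosis percentage out of biopsied patients only, so the cohort proportion needs its own line. Use these limits, not 0.37%, as what the study can exclude.
- **Comparison with 3-4%:** do not set the whole-cohort limit against this figure without noting that only part of the cohort has severe impairment.

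The cost is SAP wording, a recalculated table and an added interval, with no further patients or data. The downside is that the stated limit becomes less favourable than 0.37%, and if N is below 368 even a zero-case result will not exclude 1%.
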